### 6.2.2.3. Performance Requirements

This hypothesis test is for superiority of the cryoablation procedure over AAD's as a treatment for AF/AFL/AT in a drug-naïve population. If a two-sided log-rank test shows the difference in 12-month success rates to be less than the pre-specified alpha of 0.05, the null hypothesis (that cryoballoon ablation has similar 12-month efficacy rates compared to AAD therapy) will be rejected in favor of the alternative hypothesis (that 12-month success rates for subjects treated with cryoballoon ablation is greater than for those treated with AAD's).

### 6.2.2.4. Analysis Methods

The probability of a subject achieving success at 12 months (365 days) will be estimated using Kaplan-Meier survival analysis. The standard error will be approximated using Greenwood's formula. A two-sided 95% log-log confidence interval for the probability will be constructed. A log rank test with  $\alpha = 0.05$  will be used to assess whether the failure rate differs between treatment groups.

Day 0 is defined as either the day of the index cryoablation procedure or the day in which AAD drug therapy is initiated. For subjects with treatment failure, the survival date will be set to the date of the treatment failure. For subjects without treatment failure through 12 months, those subjects will be censored at the last study contact date recorded on a CRF, which may include the last study visit, the exit date, or death date. If a subject without a treatment failure is lost to follow-up, the censoring date will be set to the last recorded study visit date. If treatment failure occurs on the day of index treatment, survival time will be set to 0.5 days.

If an occurrence of documented AF/AT/AFL resulted from rhythm monitoring that was initiated at the 12-month visit, then the date of occurrence used in the Kaplan-Meier analysis will be the minimum of 365

days from the cryoballoon ablation procedure/date of AAD initiation, or the actual date of occurrence. This allows counting of all AF/AT/ AFL events found at the 12-month follow-up, even if the follow-up occurred after 365 days post-ablation but still within the visit window. Events found at 12-month visits outside of the window will be censored at the previous follow-up and described in deviation listings.

The survival curves from 0 to 12 months will be presented for both treatment arms.

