11.1.1. Modes of Data Collection

Multiple modes of data collection may be employed to support the collection of required visit data at the 3 and 6 month visits. This includes such methods as:

- In-office patient clinic visit
- Direct to patient contact (i.e. telephone, email, mail contact, etc.)
- Remote technology transmissions/uploads

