11.2. Medications

Information regarding drugs prescribed to treat atrial arrhythmias will be collected, including the purpose for their use/reason for modification, and start and stop dates. Information regarding anticoagulation medications will be collected, including start and stop dates.

Control Arm (AAD): Subjects must initiate a Class I or III AAD within 30 days of randomization. It is recommended that AADs be initiated as soon as possible after randomization, with a target of within 14 days. The investigator should choose the appropriate AAD per his or her standard of care; however, amiodarone should only be used if other AADs were not tolerated or failed. The 2014 AHA/ACC/HRS

⁴ Subjects shall submit ECG transmissions weekly and whenever symptoms occur after the AAD optimization/post-ablation blanking periods through 12 month follow-up.

Guideline for the Management of Patients with AF should be consulted for AAD prescriptions. Modifications to AADs (type or dosage increase) may be made for up to 90 days after AAD initiation. This is referred to as the AAD optimization period. Dosing of AADs can be individually tailored until the end of the AAD optimization period. After the optimization period, further AAD therapy optimization or change should be avoided or at least allowed only up to physicians' discretion to guarantee the safety of the patients. The possible concomitant use of beta blockers can still be optimized after the optimization period.

Treatment Arm (Cryoablation): Subjects may be prescribed Class I or III AADs for up to 80 days post-ablation procedure at the discretion of the Investigator. Subjects must stop taking all Class I or III AADs before day 81 post-ablation. Use of amiodarone is not permitted.

Anticoagulation requirements for all subjects:

Anticoagulation pre-procedure should be determined based upon the subjects CHA₂DS₂-VASc score.

- a. Oral anticoagulants are required if the subject has had a prior stroke or TIA, or if the subject has a CHA₂DS₂-VASc score ≥ 2 . When anticoagulation is required, subjects must take it for at least 21 days prior to an ablation procedure.
- b. Oral anticoagulants are not required for subjects with nonvalvular AF and a CHA₂DS₂-VASc score of 0 or 1.

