11.5.12. Ambulatory Monitoring

Market- released ambulatory monitoring equipment will be distributed by a core lab to centers after activation has occurred. Subjects will be provided with a small patient-activated electronic ambulatory

monitoring device after the AAD optimization (control arm) or post-ablation blanking period (treatment arm) ends. This device will serve two functions:

- 24 hour continuous monitoring: This is traditionally done using a Holter monitor. The investigative site personnel will apply the device patches for the subject during the subject's 6 month visit and train the subject how to apply the device. The subject will be asked to apply the continuous monitoring patches themselves prior to the 12 month study visit. Additionally, subjects may be asked to perform 24 hour continuous monitoring on their own if they miss a scheduled study visit.
- Patient-activated mode: Subjects will be asked to transmit ECG data weekly and whenever they experience AF symptoms. This mode does not require adhesive patches; the subject simply holds the device to his or her chest for a short period of time.

In both modes, the data automatically transmits to the core lab via a secured cell phone connection.

The core lab will manage maintenance, calibration and tracking of the ambulatory monitoring equipment. The core lab will be responsible for adjudication of rhythm documentation for the primary efficacy objective of the study. The core lab will send the results of all ambulatory monitoring analyses to the Investigators for appropriate follow-up, if necessary, and assessment for adverse event reporting.

Subjects will return the ambulatory monitoring equipment at the 12 month follow-up visit.

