11.9. Deviation Handling

A study deviation is defined as an event within the study that did not occur according to requirements specific to the CIP or CTA. Every attempt must be made to avoid study deviations. Prior approval by Medtronic is expected in situations where the Investigator anticipates, contemplates, or makes a conscious decision to deviate. In countries following ISO 14155:2011, prior approval for study deviations will be reported to local authorities and ethics boards per local requirements. If the deviation affects subject's rights, safety and well-being, or the scientific integrity of the study, prior approval from ethics board and/or competent authority (CA) is also required, depending on local legislations. Prior approval is not required when a deviation is necessary to protect the safety, rights, or well-being of a subject in an emergency or in unforeseen situations beyond the Investigator's control (e.g. subject failure to attend scheduled follow-up visits, inadvertent loss of data due to computer malfunction, inability to perform required procedures due to subject illness). Subjects' failure to submit ambulatory monitoring transmissions per the CIP do not require a deviation to be reported. Ambulatory monitoring transmission compliance will be tracked by Medtronic personnel and the Core Lab.

For medically justifiable conditions which preempt a subject's ability to complete a study required procedure, it may be permitted to report only one deviation which will apply to all visits going forward. This may also apply for other unforeseen situations (e.g. the subject permanently refuses to complete a study required procedure and the data will not contribute to the primary endpoint analysis.). However, prior approval from Medtronic is required for such situations.

All study deviations must be reported to Medtronic regardless of whether they are medically justifiable, pre-approved by Medtronic, an inadvertent occurrence, or taken to protect the subject in an emergency. The description of the deviation and justification must be documented and submitted to Medtronic via eCRF completion.

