#### 6.2.2.2. Endpoint Definition

A treatment success is the opposite of a treatment failure.

A subject is considered a treatment failure if he/she experiences any of the following:

- Acute procedural failure (treatment arm only), which is any of these:
  - Inability to isolate all accessible targeted pulmonary veins (assessed for entrance block and, where assessable, exit block) during the index ablation procedure, OR
  - Left atrial non-PVI ablations including but not limited to, ablation of linear lesions, OR
  - Use of a non-study device in the left atrium.
- Documented AF/AT/AFL on ambulatory monitoring/12-lead ECG after the 90-day post-ablation blanking period (treatment arm).
  - Minimum of 30 seconds on ambulatory monitoring or 10 seconds on 12-lead ECG.
  - Note: Documented occurrence and treatment of typical right-sided cavotricuspid isthmus dependent atrial flutter is not considered a failure if confirmed by entrainment maneuvers during EP testing.
- Any subsequent AF surgery or ablation in the left atrium.
- Any subsequent cardioversion after the 90-day post-ablation blanking period.
- Class I or III antiarrhythmic drug (or sotalol) use after the 90-day blanking period (treatment arm only).

The blanking period is defined as the first 90 days after the index ablation procedure (treatment arm) or AAD initiation (control arm). Recurrences of atrial arrhythmias during the blanking period will not be counted in the determination of the first clinical failure for the primary endpoint. Within the 90-day blanking period, recurrent arrhythmias can be managed with medications or cardioversions.

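### Efficacy censoring follows contact and visit dates, not rhythm recordings: a lost subject's follow-up depends on outcome, and time in contact without recordings counts as arrhythmia-free

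*SAP*

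**What the plan says.** SAP 6.2.2.4 and protocol 15.1.5 give the same two rules for subjects without treatment failure.

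- In general, "those subjects will be censored at the last study contact date recorded on a CRF". This may be a visit, exit or death date.
- For those lost to follow-up, "the censoring date will be set to the last recorded study visit date".

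A failure is dated when it occurs. Neither rule mentions a rhythm recording.

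The rhythm component (SAP 6.2.2.2) exists only if it is documented: "Minimum of 30 seconds on ambulatory monitoring or 10 seconds on 12-lead ECG". Between visits this rests on the device. Protocol Table 5, footnote 4, says "Subjects shall submit ECG transmissions weekly and whenever symptoms occur after the AAD optimization/post-ablation blanking periods through 12 month follow-up", and protocol 11.5.12 says "In both modes, the data automatically transmits to the core lab via a secured cell phone connection".

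Under protocol 11.9 a subject's "failure to submit ambulatory monitoring transmissions per the CIP do not require a deviation to be reported", although the sponsor and core lab track compliance. Protocol 11.1.1 lets the 3 and 6 month visits use other modes of data collection, including telephone, mail and remote upload. The 12 month visit is an office visit with a 12-lead ECG and 24-hour monitoring (protocol 11.5.8.4).

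**The concern.** The censoring date should not depend on whether the subject failed, and time should count as arrhythmia-free only if an arrhythmia could have been seen. Each rule misses one of these conditions, in different subjects.

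1. **Lost subjects.** Someone may keep transmitting for weeks after the last visit. AF in that gap is an event on its own date. If there is no AF, the subject is censored back at the visit and the gap vanishes from the risk set. Events are kept and event-free time is dropped, so estimated success is too low. It also sits badly with protocol 11.10, which says that all data up to exit will be used.
2. **Subjects in contact without recordings.** They stay in the risk set as AF-free until last contact, so estimated success is too high. The tipping-point analysis in SAP 6.4.1 changes only observations censored before day 365, so it cannot reach those still in contact at day 365.

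Both success estimates are at stake and, if monitoring compliance differs between the arms of this unblinded trial, so is the log-rank comparison.

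**Working it through.** **Inputs.** SAP 7.1 gives 12-month success of 69.9% (cryoablation) and 45.9% (AAD), two-sided alpha 0.05, 90% power and 10% attrition. Visit windows come from protocol Table 6. The documents give no monitoring-compliance rate, so every lapse rate below is an assumption.

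**The plan's own figure.**

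- n per arm = [1.960·√(2 × 0.579 × 0.421) + 1.282·√(0.699 × 0.301 + 0.459 × 0.541)]² / 0.24² = (1.368 + 0.868)² / 0.0576 ≈ 86.8, so 87 per arm and 174 in total.
- 174 / 0.9 = 193.3, so 194 randomized.

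Both agree with the SAP. They are not in dispute and serve only to anchor the rates.

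**Failure model (assumed).** No failures to day 90, then a constant hazard λ = −ln(S) / 275, where S is success at day 365.

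- AAD: 0.7787 / 275 = 0.002832 per day.
- Cryoablation: 0.3581 / 275 = 0.001302 per day.

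**Mechanism 1, lost subjects.** Simulated Kaplan-Meier estimates, with loss uniform over days 100–365, transmissions until loss, and 3 and 6 month visits at days 100 and 180:

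| Loss | Arm | Last-visit rule | Censored at loss | Shortfall (points) |
|---|---|---|---|---|
| 10% | AAD | 44.97% | 45.89% | 0.92 |
| 10% | Cryo | 69.15% | 69.86% | 0.71 |
| 20% | AAD | 43.95% | 45.95% | 2.00 |
| 20% | Cryo | 68.29% | 69.85% | 1.56 |

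Each event-free lost subject forfeits about 67 (AAD) to 72 (cryoablation) monitored days. If loss is instead spread over the whole year, about 265/365 = 0.73 of it falls after day 100. The shortfalls scale to roughly 0.7 and 0.5 points at 10% loss, and 1.5 and 1.1 at 20%.

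**Mechanism 2, in contact but unrecorded.** Suppose a share q stops all recording at a time uniform over days 111–365, stays in contact to day 365, and later AF is never documented. Reported success is S + q(M − S), where M is the mean probability of being failure-free at the stopping time:

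M = [exp(−21λ) − S] / (254λ)

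- AAD: M = (0.9423 − 0.459) / 0.7192 = 0.672. With q = 20%: 0.459 + 0.2 × 0.213 = 50.2%.
- Cryoablation: M = (0.9730 − 0.699) / 0.3308 = 0.828. With q = 20%: 0.699 + 0.2 × 0.129 = 72.5%.

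Simulation gives about 50.0% and 72.4%, the same within sampling error. The arm difference falls from 24.0 to about 22.3 points.

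**The test.** Simulated log-rank, 105 per arm, lapse uniform over days 91–365, later AF never documented:

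| Scenario | Lapse, AAD / cryo | Last contact | Last recording |
|---|---|---|---|
| No true difference | 30% / 30% | rejection 0.047 | 0.051 |
| No true difference | 10% / 30% | rejection 0.09 (0.084 favouring cryo) | 0.048 |
| True 24-point difference | 0% / 0% | power 0.95 | 0.95 |
| True 24-point difference | 30% / 30% | power 0.90 | 0.92 |
| True 24-point difference | 30% / 10% | power 0.82 | 0.93 |

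**The case against.** The strongest reply is that last contact suits much of this composite. Cardioversion, repeat ablation and, in the cryoablation arm, antiarrhythmic drug use are learned through contact. That stands, and it rules out simply replacing the primary rule. If every event-free subject were censored at the last recording while later failures still counted, follow-up would again depend on outcome: with 20% lapsing over days 111–365 and 30% of later failures counted, success reads about 44.9% and 69.1%.

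Second, mechanism 2 is narrow. A reader might infer that anyone who stops weekly transmissions is miscounted and that last-recording censoring would repair it. The documents do not support this. A subject who completes month 12 has an ECG and a 24-hour recording at about day 365, so the two censoring dates coincide and the earlier gap counts as AF-free under either. Nor does remote data collection establish that ECGs are skipped: 12-lead ECGs remain listed at the 3 and 6 month visits.

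Third, a reader might infer that compliance will differ by arm because missed transmissions are not deviations. That does not follow; compliance is tracked, and an unblinded design makes a difference possible, not shown.

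Fourth, lost subjects do enter the tipping-point analysis, and the last-visit rule moves the arm difference by only about 0.2 points at 10% loss (0.92 − 0.71). Both are true. The core lab also enters CRFs (protocol 11.8), so a transmission might pass as CRF-recorded contact, but the lost-subject rule explicitly says visit. Finally, parts of the SAP are redacted, so one can say only that the visible text has no compliance summary or analysis of unmonitored time.

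**Conclusion.** The concern holds in limited form. Censoring is not tied to rhythm assessment.

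- For lost subjects the rule makes follow-up depend on outcome. It understates success by about 0.7–0.9 points (AAD) and 0.5–0.7 (cryoablation) at the planned 10% attrition, if all of it is loss to follow-up, and by about 1.5–2.0 and 1.1–1.6 at 20%.
- For subjects in contact with no further recordings, month 12 included, it overstates success: about 50% and 72.5% against 45.9% and 69.9% if 20% lapse and none of their later AF is documented.

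These sizes rest on the exponential model, stopping or loss unrelated to AF risk, and the assumed lapse rates. A general claim of type I error inflation would go too far: equal lapse works against the sponsor and leaves the error near 0.05, and inflation requires unequal lapse with more in the cryoablation arm. This is worth correcting before analysis, but it does not invalidate the primary comparison.

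**What to change.** In SAP 6.2.2.4:

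1. Censor lost subjects without failure at the later of the last visit and the last core-lab-evaluable recording, by the same rule in both arms.
2. Keep last contact as the primary rule for all other subjects.
3. Pre-specify a sensitivity analysis that censors every subject without a prior failure at the last evaluable recording (12-lead, 24-hour or transmission), capped at day 365, and does not count failures after that date. In the simulated lapse scenarios this returns about 46% and 70%.
4. Report by arm the share of expected weekly transmissions received, and of 12-month ECGs and 24-hour recordings obtained. The sensitivity analysis cannot correct a gap that ends with a month-12 recording, so this table is needed to judge such gaps.

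Protocol 15.1.5 should be aligned with item 1. The cost is SAP wording, a merge of core-lab dates already collected, a little more analysis work and slightly fewer person-days in the sensitivity analysis. No new data are needed.

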11.5.8. Scheduled Follow-up Visits

After the index cryoablation procedure (treatment arm) or AAD initiation (control arm) is reported in the study database, the database will calculate the target dates and windows for each visit to the site. Should a subject miss a visit or the visit fall outside the pre-specified window, a study deviation must be reported and the original follow-up schedule maintained for subsequent visits.

Data analyses include follow-up visits, regardless of whether the visit occurs within the window. Therefore, a late visit is preferred over a missed visit but must be accompanied by a deviation. Follow-up visit windows are listed in Table 6 and are based on days post-index procedure or AAD initiation.

Table 6: Follow-up Visit Windows

| Occurrence/ Visit | Window (Calculated days post-procedure or AAD initiation) | |
|---|---|------------|
| | Window Start | Window End |
| Randomization | -30 days | Day 0 |
| Index Cryoablation Procedure/ AAD initiation | Day 0 | Day 0 |
| 1 month | 31 days | 51 days |
| 3 month | 91 days | 111 days |
| 6 month | 165 days | 195 days |
| 12 month | 365 days | 395 days |

The following activities will occur at the follow-up visits:

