11.5.8.4. Twelve month Office Visit

- Review medications
- Adverse event assessment
- Review symptoms suggestive of recurrent AF/AT/AFL
- Health care utilization assessment- collect information about hospitalizations or emergency department visits experienced by the subject since the last visit
- 12 lead ECG
- 24h continuous ECG monitoring with ambulatory monitoring equipment. The subject will be instructed to apply the continuous monitoring patches and complete the 24 hours of continuous monitoring within 7 days prior to the 12 month visit. It is recommended that the study personnel call the subject to remind them of this requirement. If the subject is not able to apply the device prior to the visit, it may be applied by study personnel at the 12 month visit.
- EQ-5D and AFEQT Questionnaires
- Collect the ambulatory monitoring equipment and return to Medtronic (or designee). If the subject did not perform the continuous monitoring prior to the 12 month visit, apply the device to the subject to complete 24 hour continuous monitoring. Give the subject instructions on how to return the equipment.
- Chest X-ray, including inspiration and expiration films, is required for subjects whose PNI was unresolved at the 6 month visit
- In the case of suspected PV stenosis, Magnetic Resonance Imaging (MRI) or Computerized Tomography Scanning (CT scan) is required. It is not required at this visit if it was already completed at an earlier visit and PV stenosis was confirmed.
- Inform the subject they have completed the study

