15.1.5. Analysis Methods

The probability of a subject achieving success at 12 months (365 days) will be estimated using Kaplan-Meier survival analysis. The standard error will be approximated using Greenwood's formula. A two-sided 95% log-log confidence interval for the probability will be constructed. A two-sided log rank test with $\alpha = 0.05$ will be used to assess whether the failure rate differs between treatment groups.

Day 0 is defined as either the day of the index cryoablation procedure or the day in which AAD drug therapy is initiated. For subjects with treatment failure, the survival date will be set to the date of the treatment failure. For subjects without treatment failure through 12 months, those subjects will be censored at the last study contact date recorded on a CRF, which may include the last study visit, the exit date, or death date. If a subject without a treatment failure is lost to follow-up, the censoring date will be set to the last recorded study visit date. If treatment failure occurs on the day of index treatment, survival time will be set to 0.5 days.

If an occurrence of documented AF/AT/AFL resulted from rhythm monitoring that was initiated at the 12-month visit, then the date of occurrence used in the Kaplan-Meier analysis will be the minimum of 365 days from the cryoballoon ablation procedure/date of AAD initiation or the actual date of occurrence. This allows counting of all AF/AT/ AFL events found at the 12-month follow-up, even if the follow-up occurred after 365 days post-ablation.

The survival curves from 0 to 12 months will be presented for both treatment arms.

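### The rule that dates 12-month AF/AT/AFL back to day 365 omits the home recording made before the visit, so AF on one made after day 365 is left out of the 12-month success rate

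*SAP*

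**What the plan says.** **Estimate and default dating.** SAP 6.2.2.4 states: "The probability of a subject achieving success at 12 months (365 days) will be estimated using Kaplan-Meier survival analysis". It also states: "For subjects with treatment failure, the survival date will be set to the date of the treatment failure".

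**The exception.** SAP 6.2.2.4 begins it with "If an occurrence of documented AF/AT/AFL resulted from rhythm monitoring that was initiated at the 12-month visit". Such an event is dated at day 365 or its actual day, whichever is earlier. Protocol 15.1.5 uses the same trigger and gives the purpose: "This allows counting of all AF/AT/ AFL events found at the 12-month follow-up", even when that follow-up takes place after day 365. The SAP adds that the visit must be within its window, and that events found at out-of-window visits are censored at the previous follow-up. Protocol 15.1.5 has no such condition.

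**The window.** Protocol Table 6 (section 11.5.8) reads "12 month | 365 days | 395 days".

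**The recording.** Protocol 11.5.8.4 tells subjects to "complete the 24 hours of continuous monitoring within 7 days prior to the 12 month visit". Protocol 11.5.12 agrees: "The subject will be asked to apply the continuous monitoring patches themselves prior to the 12 month study visit". If the subject cannot apply the device beforehand, "it may be applied by study personnel at the 12 month visit".

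**The concern.** The last scheduled visit falls on or after the day at which the endpoint is read, so some back-dating rule is needed. The one written is triggered by where the monitoring began. It covers the fallback (recorder put on at the visit) and omits the default (recorder worn at home before the visit).

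Three things are at stake.

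- **Which failures enter the primary estimate.** Table 5 schedules the 24-hour recording only at 6 and 12 months, so part of one of two continuous assessments may fall outside the day-365 rate.
- **Consistency between subjects.** Two subjects with AF on the same day after day 365 can be classified differently at day 365, depending only on whether the patch was applied at home or in the clinic.
- **Reproducibility.** SAP section 8 requires independent programming of the primary analyses. A programmer following the trigger and another following the stated purpose would obtain different 12-month rates.

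The SAP handles the same problem more fully elsewhere. HCU events after day 365 but before an in-window 12-month visit are included (6.2.5.1.2), and safety events first observed at an in-window visit count at one year (6.2.3.4). The efficacy wording therefore looks like a drafting gap rather than a choice.

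**Working it through.** **1. The plan's own figure.** The plan gives no figure for this rule. The nearest is the efficacy sample size in SAP 7.1, which uses success rates of 69.9% and 45.9%, two-sided alpha 0.05 and 90% power. The pooled-variance formula without continuity correction, n = [1.960·√(2·0.579·0.421) + 1.282·√(0.699·0.301 + 0.459·0.541)]² / 0.24², gives 86.8, so 87 per arm and 174 in total. Power at 87 per arm is 0.9005, and 174/0.9 = 193.3, so 194. All three match the SAP. None depends on the dating rule.

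**2. What the rule covers, read literally.**

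| AF/AT/AFL found on | Date used | Counted in the day-365 rate? |
|---|---|---|
| Home recording on or before day 365 | Actual day | Yes |
| Home recording after day 365 | Actual day | No |
| Recorder applied at an in-window visit | min(365, actual day) | Yes |
| 12-lead ECG at an in-window visit | min(365, actual day) | Yes |
| Weekly or symptomatic transmission after day 365, before the visit | Actual day | No |

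Example: with a visit on day 385, AF on a home recording made on day 380 is dated 380. AF on a recorder applied at that visit is dated 365.

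**3. Share of home recordings dated after day 365.** Inputs: visit day V from 365 to 395 (Table 6) and a recording k = 1 to 7 days earlier (11.5.8.4). A recording is affected if V − k > 365. The number of affected lags out of 7 is:

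- V = 365 or 366: 0
- V = 367 to 372: 1, 2, 3, 4, 5, 6 (sum 21)
- V = 373 to 395: 7 each

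The documents do not give the spread of visit days or lags. Taking lags as even over 1 to 7:

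| Visits (assumed) | Affected / all pairs | Share |
|---|---|---|
| Day 365 or 366 only | 0 / 14 | 0% |
| Even over 365 to 372 | 21 / 56 | 37.5% |
| Even over 365 to 374 | 35 / 70 | 50% |
| Even over 365 to 380 | 77 / 112 | 69% |
| Even over 365 to 395 | 182 / 217 | 83.9% |
| Day 373 or later only | all | 100% |

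For visits even over the whole window, the share is 74.2% (23/31) if every recording is made 7 days before, and 93.5% (29/31) if every one is made 1 day before.

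**4. Effect on the day-365 rate.** Overstatement relative to the rule's purpose ≈ f × s. Here f is the share of subjects whose first failure is on a home recording for the 12-month visit, and s is the share from step 3. The documents give no f; 1% to 5% is assumed.

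- s = 37.5%: 0.4 to 1.9 points
- s = 83.9%: 0.8 to 4.2 points

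**The case against.** The case on the other side has several parts.

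- **The intent is plain.** The sentence after the rule states its purpose, and Table 5 and section 11.5.8.4 list the 24-hour recording under the 12-month visit. An analyst could fairly treat a home recording as 12-month monitoring. This shows what was meant, but it does not settle the text: section 11.5.8.4 itself separates recordings made before the visit from devices applied at it.
- **Most home recordings need not be affected.** A reader might infer that they are. This holds if visits spread over the window, but not if they cluster in its first week. The documents give no visit timing, so it is not established.
- **The purpose is not met only for subjects who ignored the instruction.** The visit ECG is covered for everyone, and home recordings made by day 365 count at their own date. Application at the visit is a permitted alternative.
- **The primary test may be untouched.** A reader might infer that the p-value loses these failures. Neither document cuts the log-rank test at day 365, and the fictional dataset in SAP 6.4.1 contains an AAD event on day 371. An uncut test would keep them. It would then use failures that the 12-month estimate omits, although SAP 6.2.2.3 describes the test in terms of 12-month success rates.
- **Both arms move the same way.** Suppose 2% to 10% of still event-free subjects in each arm show AF on this recording, with s = 83.9%. The planned difference of 24.0 points would then change by 0.839 × 24.0 × 2% = 0.4 to 0.839 × 24.0 × 10% = 2.0 points. The rule is the same in both arms and a core lab adjudicates rhythm, so no bias towards one arm is shown by the unblinded design alone.
- **Overstatement is relative.** AF first seen on day 380 is not a failure by day 365 in the strict sense. The departure is from the plan's declared convention.

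All but the first limit the size of the problem. None removes the conflict between trigger and purpose.

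**Conclusion.** The rule is wrong as written. Its trigger excludes the recording that the protocol makes standard, and so defeats its stated purpose whenever that recording is made after day 365.

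The share of home recordings affected runs from 0% to 100% with visit timing: 37.5% for visits even over days 365 to 372, and about 84% for visits even over the window. Both figures assume lags spread evenly over 1 to 7 days. If 1% to 5% of subjects first fail on this recording, the 12-month success rate is about 0.4 to 4.2 points higher across these two scenarios than the stated purpose implies.

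The effect that follows from the text is on the 12-month estimate in each arm. The documents do not support the claim that the primary p-value loses these events, or that most home recordings are lost. Weekly and symptomatic transmissions, which continue to the 12-month follow-up (Table 5, footnote 4), have the same gap.

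**What to change.** Before the data are analysed, amend protocol 15.1.5 and SAP 6.2.2.4 together:

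1. Date AF/AT/AFL at min(365, actual day) when it is found on the 12-month 24-hour recording, made within 7 days before or at a 12-month visit that is within its window, or on that visit's ECG. This keeps the SAP's in-window condition and adds it to the protocol.
2. State one rule, the same in both arms, for weekly and symptomatic transmissions between day 365 and the in-window visit.
3. State that the log-rank test and the Kaplan-Meier estimate use the same event dates.

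The cost is a few sentences in each document and a small change to the event-date derivation. The planned sample size does not change. The downside is that reported success may be slightly lower in both arms.
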